Buenos Aires, March 4th, 2023

Research Project for the Control of Myopia Progression
using Peripheral Defocus Glasses (MYOFIX STUDY)

Sociedad Argentina de Oftalmología
Ethics Committee.

Dear [name].

We are writing to request that you kindly consider the ethical aspects of the following research study in clinical ophthalmology aimed at halting the progression of myopia with special myopia control glasses, as referred to in this request.

[name]

[name]

MYOPIA CONTROL STUDY

Study on the Tolerance and Efficacy of the Use of Peripheral Defocus Spectacles for the Control of Myopia Progression in Children and Adolescents.

PRINCIPAL INVESTIGATOR. [name]

ASSOCIATE INVESTIGATORS. Drs. [name], [name], [name], [name], [name], [name],

RESEARCH CENTER. Office Dres. [name]. [name].

TYPE OF STUDY

A longitudinal, prospective, interventional, clinical ophthalmology research study to evaluate the tolerability and efficacy of intervention with the use of a nationally designed eyeglass to control the progression of myopia in childhood and adolescence.

PROBLEM STATEMENT JUSTIFYING THE STUDY

Refractive errors are considered the second leading cause of visual impairment worldwide.¹ Global estimates indicate that approximately 312 million in 2015 are short-sighted, figure that could rise to 324 million by 2025¹ and a 4,758 million for 2050.^{2,3} Geographically, the distribution of myopia in the world varies significantly,⁴ with figures ranging from 6.1% for Morocco (Africa) up to 96.5% for Korea, (Asia).^{3,5,6} Ethnic contrast and lifestyle habits in Asian and African populations are potential associated factors, although such a claim remains to be fully elucidated.³

In East Asia, the prevalence of myopia reaches 80%,^{7,8} in Europe is lower, at 47.2% for the group between 25 and 29 years of age for the year 2015.⁹ In Latin American populations such as Brazil, the prevalence in the adult population was of 29.7% for the year 2009.¹⁰ In the United States, there is evidence of a disproportionate increase in the number of myopes, with a prevalence of between 25 and 41.6% between the ages of 12 and 54 years for the year 2011.¹¹

In the report of the countries that make up the Ibero-American Epidemiological Network for Eye and Eye Health, for the period 2009-2010, the lowest prevalence for children was reported in Argentina (1.2%) and the highest in Ecuador with 25.2%. The low values in Argentina were determined only in rural areas and this is why they are so contrasting with the rest of the countries in the network. Another study from Argentina conducted in office workers in the city of Buenos Aires has found a prevalence of myopia of approximately an 25%.¹² In Colombia, the diagnosis of myopia in the 2009-2010 period was 21% and 22%, respectively, with a higher prevalence in the 5 to 14 years age group, followed by the 15 to 44 years age group.¹³

Myopia progression can trigger pathologic changes in the eyeball that affect structures such as the lens, retina, choroid and macula. Myopia progression doubles the risk of nuclear cataract,¹⁴ open-angle glaucoma,¹⁵ maculopathy, choroidal neovascularization and retinal detachment.¹⁶ These degenerative changes are the most frequent cause of vision loss with irreversible blindness.¹⁷ and are associated with refractive values of more than 5-6 diopters of myopia in adult life.^{6,18-21}

Research work on preventive treatments, to date, is generally conducted on children 6-12 years of age,^{22,23} and a few unpublished studies of natural history or treatment effectiveness in

adolescents are ongoing. In addition, children who begin with their myopia between the ages of 5 and 7 years of age when they do not yet read intensely, they often have genetic myopia that may develop high myopia.²⁴ In turn, these children are the ones most at risk for adult disability due to myopic maculopathy.¹⁷ It has been suggested that these children should be treated according to the myopia consensus of the SAOI Myopia Study Group with atropine 0.01% or 0.05% to prevent such rapid progression.²⁵ Children over 8 years of age progress at a slower rate, even more slowly as they get older.²⁶

In recent years, several treatments have been developed to halt the progression of myopia at school age, among which the daily instillation of 0.01% atropine drops stands out for its efficacy.²⁷ Despite the high dilution, there are reservations among pediatric ophthalmologists about the toxic effect that a daily instilled drop could have from elementary school age to 25 - 30 years of age, and therefore there is interest in developing other less invasive therapeutic methods.²⁷ In this regard, the different types of spectacles and peripheral defocus contact lenses have recently shown good effectiveness in several randomized and controlled clinical trials against the natural history of progression.²⁸ In some cases these studies have been ongoing for 5 years and have shown similar effectiveness to atropine (60% reduction in progression) as presented at the last International Myopia Conference in Rotterdam last month. Studies combining both therapeutics are already underway with modest results of an increase in effectiveness to 70% reduction of progression (presented at the same Conference). These peripheral defocus lenses and peripheral contrast decreasing lenses could replace formal glasses in the case of myopic children, since formal glasses could favor the progression of myopia since they produce peripheral hyperopic defocus.²⁹ Studies in monkeys from 2005 by Earl Smith III showed that the area surrounding the fovea was in control of eye growth, as compensation of the imposed lenses occurred equally even with the laser ablated fovea.³⁰ Thus, attention began to be paid to where the

images fell in the mid-periphery and was tested on animals and humans with positive addition multizone defocus lenses that place part of the image plane in front of the retina, thus slowing down ocular growth.³¹ Since 2011, several studies have been presented showing how myopia slows down its progression with the adaptation of multizone defocus contact lenses with positive additions in the periphery.³¹ There are even multifocal glasses for myopia control such as Essilor's Varilux for more than 20 years, which follow the same principle although they are not as effective (20% effect) and therefore have not been widely used.³²

Currently there are several patented commercial brands that offer (in Asia and Europe) multizone defocus lenses with positive defocus in the periphery to stop the progression of myopia. None of them is still on sale in our country, but CooperVision's Proclear multifocal contact lenses, designed to treat presbyopia in adults, of which there is a variety with a center for distance (like the lenses tested for myopia) are sometimes accessible in our environment with the difficulty that the population of opticians and ophthalmologists are mostly unaware of their possible use and do not recommend them. These same lenses were used "off-label" in a clinical study in 2013 in England showing modest results with a 40% decrease in progression.³³

CURRENT STATE OF RESEARCH

At the aforementioned International Conference a month ago, Mark Bullimore³⁴ and other researchers pointed out that it has become a problem to conduct randomized controlled studies against natural history because it is unethical to leave them to their own devices when off-label treatment with 0.01% atropine has already been accepted in various consensuses.^{25,28,35,36} This diluted drug has already been approved in Singapore, Japan and India where it exists in commercial form, but in other countries it is only available as a

compounded formula.

Thus, at the Conference, several investigators showed that ongoing studies with a natural history control group see their number of cases decrease with follow-up as patients drop out to seek medical care to prevent myopic progression with the means available today. These means are dilute atropine drops, daily outdoor exposure,³⁴ reading with inverted contrast,³⁵ special contact lenses for myopia control, peripheral defocus glasses and contrast reduction glasses, both designed for myopia control. In our environment, only the first three are available to the population. That is, we can recommend more outdoor exposure, reading with inverted contrast (not yet tested in a randomized study) or instilling diluted atropine drops off-label.

Due to the problem of attrition in the control group, it has been suggested in the last International Myopia Conference that controlled field studies be performed by a virtual group, without performing a non-inferiority study, since atropine 0.01% could not be taken as gold standard because it is not yet approved and as we said, it is off-label in Argentina. Data on progression in Asia or Europe could be used for this virtual control group, but it would be more convenient to have a virtual control group in one's own living environment. In the case of our country there is already a possible control group of 114 children of 12 years of age on average who were followed up with cycloplegia during the years pre-pandemic and from which it is known that the progression was from 0.43+/-0.52 diopters in one year.³⁶

It is thus proposed to perform a prospective clinical study in 100 children who will be enrolled when in the usual consultation for their eyeglasses control they can choose to do the treatment accessible in our environment (the diluted atropine drop) or a treatment that is possibly equally effective with special glasses designed in our environment. It is

expected that there will be similarity of effect on progression because the lens is based on the principles of defocusing of eyeglasses and contact lenses already proven by the international industry.³⁷ Our lens has the characteristic of being much simpler in its carving and construction, making it more economical for our environment where it has already been presented from the theoretical point of view.³⁸

Moreover, the special myopia control spectacle lacks the possible toxic effects of a drop instilled in the eye for many years until emerging adulthood. In addition, to avoid including children who may have rapid progressions to high myopia, treatment will be offered only to children over 8 years of age. In our environment, where children are outdoors a lot, the progression is slower than in Asian countries and is around -0.50 diopters per year, as we said.³⁶ A strong myopia is the one that exceeds -5.00 diopters.³⁹ Thus the risk for a child included in this project is to progress -0.25 diopters in six months (the resolution limit of the measurement method), so each child who does not respond well with arrest of progression at six months may be removed from the protocol and switched to atropine treatment.

Given the above-mentioned background, the following study has been designed to evaluate the arrest of myopia progression with the daily use of nationally designed glasses, comparing such progression with a virtual control group of similar age in a population of myopic children and adolescents of the same environment in our country.

WORKING HYPOTHESIS

The nationally designed lenses can be as effective as the proven international industry designs that have been subjected to controlled trials against natural history of the disease.

PURPOSE

To treat a group of consecutive volunteer patients who choose between the affordable treatment in our environment (daily diluted atropine drops for several years) or the special lenses for myopia control designed by the National Industry. The purpose is to compare the progression during one year with the national lenses with respect to the progression with the foreign lenses and/or with the natural history of a virtual control group.

OBJECTIVES

Primary

To assess whether the intervention with locally designed spectacles is well tolerated and adhered to with daily use in childhood and adolescence.

Secondarily

To assess whether intervention with locally designed glasses can control myopia progression in childhood and adolescence.

DEFOCUS GLASSES OF NATIONAL DESIGN

The design of the national defocus lens is based on the original design presented by Carly Lam,⁴⁰ with a 9 mm central zone for distance correction and a correction ring with a +3.50 dioptre defocus between 9 and 32 mm in diameter to act in principle on the para foveal zone which is the one that detects the defocus that governs the growth of the eye.⁴¹ Instead of peripheral defocusing micro lenses that do not alter the visual field in the area of the 32

mm diameter ring with the treatment,⁴⁰ the national design that was presented has a uniform +3.50 diopter power zone that alters the visual field by 5% at 10 degrees from the circular shaped fovea,³⁸ as presented at the International Myopia Conference a month ago. As it is known that positive defocus in 30-40 minutes of exposure modifies the axial length (measured with Lenstar) by 10 microns due to changes in the choroidal thickness,⁴² The national design has been tested on 17 volunteer subjects showing a significant change of 11 microns in the axial length of their eyes, suggesting this pilot study (in the process of being published) that the lenses should be effective in halting the progression of myopia, as changes in the choroid are the first event in the retinal message that governs ocular growth.⁴³ This, coupled with the survey that gave a good reading tolerance in 70% of the 17 respondents within a month of wearing them, was presented at the Conference and is in the public domain. Respondents found it difficult to walk around with these lenses because they are like an executive bifocal, but tolerated them well for reading at home, with small lateral movements of the head when reading A4 texts or the computer. It is therefore our intention to do a free field test with such lenses on a larger sample.

POPULATION

Consecutive patients between 8 and 16 years of age who attend the institutions accredited for this study. These institutions will be accredited only if they can perform routine studies for myopia control (refraction exam and optical biometry).

USE OF GLASSES

Once the eyeglass prescription has been written by the ophthalmologist, the enrolled patients will be seen in opticians accredited for this study in close proximity to the

ophthalmology offices that are members of the research team. The opticians and ophthalmologists will be asked to watch a video on myopia control developed by the principal investigators where this treatment methodology is explained during the evaluation process at the center of care. The opticians will verify the optical centration in the frames chosen ad hoc, with a modern digital centration system provided by the sponsors. After 15 days, when the glasses with the correct centering are ready, the subjects will go to the optician's office to try on the glasses in that room. On this occasion, as always in these cases, the optician will evaluate the subject's adaptation and mobility in the optician's shop, instructing the child to wear the glasses at home for a couple of days and then to wear them for as long as possible.

SAMPLE AND SAMPLE SIZE

The sample size will be 50 subjects of both genders to compare with the studies abroad that consist of an n between 40 and 90 subjects and the natural history in our country that counted 114 subjects. There will be a group of subjects who will be treated with the nationally designed defocus glasses. Statistical calculation for a difference of 0.25 diopters in progression with respect to controls, for a standard deviation of 0.50 diopters gives an $n = 31$ subjects and taking into account a 20% loss to follow-up the n should equal 38 subjects in the group. Thus reaching 50 subjects exceeds expectations.

METHODS

This field study to test tolerance and percentage of effectiveness of defocus lenses in the control of myopia will include boys and girls from 8 to 15 years of age who voluntarily

agree to take the test for one year, with no ocular pathology other than myopia, with spherical equivalent (sphere + 50% of the cylinder) between -0.50 D and -5.00 D, with astigmatism less than -2.00 D in each eye, with anisometropia less than -1.00 D, with keratometry less than 47.00 D in the most curved meridian. Genetic syndromes will not be included or ruled out. A complete ophthalmologic evaluation will be performed including tonometry, fundus, subjective refraction and refraction under cycloplegia with two drops of 1% cyclopentolate instilled 5' apart and performed 40' after the last drop. Visual acuities of the subjective refraction will be greater than 8/10 in each eye. Axillary length measurements with optical biometry will be performed at the beginning of treatment at follow-up and at the end of the study. New cycloplegic refractions will be performed during follow-up and at one year of treatment. A survey of habits and history, including reading, outdoors, ON-OFF contrast use, hours of schooling, age of onset of spectacle use and family history of high myopia (also likely use of devices to monitor these habits in selected group) will be conducted. A pair of spectacles and their frames will be provided free of charge to all children studied for one year with the special addendum of peripheral defocus treatment or laser treatment for contrast reduction depending on the treated group. The children will be instructed to wear the glasses especially in front of smartphones, tablets, PC's or books at home after five o'clock in the afternoon and until going to bed, every day of the week including Saturdays and Sundays. During the rest of the day they will use their usual correction without properly updated defocus. As defocus in experimental animals has more effect in stopping experimental myopia in the afternoon than in the morning,⁴⁴ It is expected that use in the afternoon only will be sufficient to achieve the effect. On the other hand, the peripheral contrast-lowering lens that has shown good tolerance and absence of visual field alteration will be used all day long by the subjects under treatment.

All the data of affiliation, contact telephone number, date of birth, refraction under cycloplegia, axillary length and questionnaire will be entered in a centralized digital history by NOVAR developers. These data will be kept confidential. During follow-up visits, accredited professionals throughout the country will have access to upload the data required for each visit. One month after the eyeglasses are delivered, the professional will conduct a telephone survey to parents to evaluate adherence. The first stage of the study will be completed after one year and the child will be able to continue with the treatment for myopia control according to the consensus guidelines on myopia treatment of the Myopia Study Group of the SAOI (Annex I). For virtual control group, data will be taken from 114 children followed with cycloplegia by the pandemic study group during the years 2018-2019 that showed for an average age of 12 years an annual pre-pandemic progression of -0.45 D. In the present study, We expect to evaluate the progression with peripheral defocus treatment over one year of an equivalent group of children.

WORK PLANNING / GANTT CHART:

Activity	TIME IN MONTHS						
	1	2-4	5-24	25	26	27	28
Project Design	X	X					
Bibliographic search	X			X	X		
Ethics Committee Presentation		X					
Data collection			X				
Data analysis				X	X		
Preliminary results					X	X	
Final Results						X	X
Report writing							X

INCLUSION / EXCLUSION CRITERIA

All consecutive patients of both genders who freely opt for lenses of national industry will be included in the present study. All patients who present any systemic or ocular pathology that may affect their refraction measurements or their evolution will be excluded from the study. Also excluded from the protocol in the follow-up will be those patients who, even using defocus glasses, had in 6 months an improvement equal to that expected without any intervention. These patients will be treated with other options available in our environment at the time of the change. The computerized medical records system will be configured to detect such patients at the time of loading the follow-up data and will send an alert to the investigators.

EVALUATION OF TOLERANCE AND ADHERENCE

Adherence will be evaluated at the one-year follow-up and will be reported as the number of cases that failed to complete the three scheduled visits in one year with respect to the total number of cases that were enrolled in compliance with the first visit and the delivery of the spectacle. Tolerance of these glasses will be assessed with a tolerance questionnaire that is presented in the attached medical record. This questionnaire has already been tested on 24 subjects aged 18 to 24 years in a pilot trial presented at the International Myopia Conference, as explained in the previous section on the defocus spectacle, showing good tolerance in these subjects. Some tests in younger children that were performed in the last months show that tolerance is very good in them, since minors have greater plasticity and adaptability than young adults previously tested. Tolerance and adherence will be classified as GOOD / BAD, in a dichotomous way, with the cut-off according to the answer given by whether the child tolerated them well or not. On the other hand, tolerance will also be evaluated in dichotomous form with responses to reading and walking

performance.

PROCEDURES TO GUARANTEE ETHICAL ASPECTS

The anonymity of all participants will be preserved. Patients' names will be removed from the database for statistical analysis. The only ones who will know the names of the patients are the physicians involved in their primary care, and they will have to keep the information in their respective institutional medical records and enter the data necessary for the research in a web form designed by the sponsoring company.

The Declaration of Helsinki and its modifications, the Good Clinical Practices guide, the harmonization norms and the resolution of the Ministry of Health 1480/11 will be observed and taken into account as guidelines (See informed consent ANNEX VI). It is stated for the record that the principal investigator does not have any type of conflict of interest since the patenting of the defocus glasses is the responsibility of the sponsor's company.

SAFETY PRECAUTIONS

One month after the delivery of the spectacle, the principal investigator in charge will make a telephone call to the parent of the study subject conducting the tolerance survey and thus verifying adherence to spectacle use. The survey is detailed in the attached medical record and responses will be uploaded into the computerised web-based system that will be developed for this study. The system will automate the alerts for these safety calls with automatic emails sent to the principal investigator in the month of spectacle delivery.

PLAN FOR ANALYSING THE RESULTS

The results of numerical variables shall be expressed as mean and standard deviation or median and interquartile range according to whether they are normally or skewed. Nominal variables will be expressed as absolute frequency and percentage. For the comparison of numerical variables, Student's t-test or Mann Whitney U-test will be used as appropriate. Nominal variables will be compared using the Chi-square test or Fisher's exact test as appropriate. A p-value of $p \leq 0,05$.

HUMAN RESOURCES

[name] and [name] are in charge of the design and control of the research. Statistical analysis will be performed by [name]. Physicians accredited to treat patients will have to demonstrate the ability to perform routine consultations for myopia control, refraction studies under cycloplegia and optical biometry. Once accredited, they will have a username and password to upload their data into the web form. Accredited doctors will be in permanent communication with doctors [name] and [name]. There will be a myopia progression monitoring system within the computerised system that will send reports if any child progresses more than 0.25 dioptres in six months to alert researchers so that precautionary measures can be taken in such cases.

MATERIAL RESOURCES

Optotypes, Retinoscope, Autorefractometer and Biometer posters of accredited institutions.

Approximately four institutions with a high turnover of paediatric consultations are expected to be accredited for an estimated enrolment time of 6 months.

Peripheral defocus spectacles will be provided by the sponsor (NOVAR) free of charge to all study subjects for one calendar year with the possibility of extending the study for two years. At the end of the study, if the expected positive results are found, the glasses will remain in the possession of the study subjects.

FINANCIAL RESOURCES

It is considered necessary for the development of the study the free coverage by the sponsors (NOVAR) of the peripheral defocus glasses. Money will also be spent for the web form system programmers and for the two ophthalmologists in charge of the study.

The expenses of the medical consultations made by the subjects at the time of enrollment and follow-up will be paid by the medical system of each of the accredited institutions (whether these are social security or prepaid health insurance of the subjects) since no more consultations are required for the study than the three per year recommended for myopia control according to the last consensus of the Myopia Study Group of the SAOI (Annexed). No corneal or eyeball complications are expected (as with contact lenses or drops) since the glasses are a prosthesis that is not introduced into the body and acts at a distance.

CENTERS OF ATTENTION

Eight enrollment centers will be chosen. To avoid biases in the methodology and to adjust the feasibility of developing a joint protocol, training interviews will be conducted with the investigators from each center in a timely manner. The principal investigator will maintain weekly communication by telephone with each of the investigators involved in each center.

ENROLLMENT

Consecutive patients attending the above-mentioned care centres for glasses prescription will be enrolled. Family members will be informed in writing and verbally of the objectives of the study and will sign an informed consent for the study.

Subjects must be willing to participate in a study lasting 1(one) year (it will be explained to them at the beginning of the study that the free treatment materials will in principle only extend for that period).

Risks, discomforts or ethical issues related to participation:

Clinical and biometric ophthalmological studies with or without cycloplegia are routine and free of discomfort for patients.

CRITERIA FOR INCLUSION

- Patients of both sexes aged between 8 and 16 years, without ocular pathology added to myopia.

- Myopia ranges between 2.00 D and 5.00 D in both eyes.
- Refractive astigmatism less than one diopter in each eye.
- Visual acuity 20/25 or better in both eyes.

EXCLUSION AND ELIMINATION CRITERIA

Patients who do not meet the aforementioned inclusion criteria.

Patients with poor adherence to treatment demonstrated by poor compliance with follow-up interviews.

Patients whose family members do not sign the informed consent form.

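### Progression is refracted by unmasked treating physicians with no instrument fixed, so expectation can bias the treated group only, and the historical comparison cannot remove it

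*Combined protocol and SAP*

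**What the plan says.** OBJECTIVES makes tolerance and adherence primary and control of progression secondary. Progression is nevertheless the only outcome in SAMPLE AND SAMPLE SIZE: "Statistical calculation for a difference of 0.25 diopters in progression with respect to controls, for a standard deviation of 0.50 diopters". PURPOSE describes the comparison as one of progression over a year.

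There is one treated group. The comparator is a virtual control of 114 children followed in 2018-2019 (METHODS; also CURRENT STATE OF RESEARCH). No masking of child, physician, assessor or analyst is described.

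On the measurement itself, METHODS states: "New cycloplegic refractions will be performed during follow-up and at one year of treatment". It specifies the cycloplegic drops and the waiting time, but not the instrument, the number of readings or the recording step. MATERIAL RESOURCES lists "Optotypes, Retinoscope, Autorefractometer and Biometer posters of accredited institutions" without saying which device gives the study value. The visit forms (Parts I, III and IV) have fields for sphere, cylinder, axis and axial length, and none for method. HUMAN RESOURCES expects the physicians accredited to treat the children to be able to do cycloplegic refraction and to upload the data; no separate assessor is mentioned.

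CURRENT STATE OF RESEARCH gives a child's risk as to "progress -0.25 diopters in six months (the resolution limit of the measurement method". Axial length by optical biometry is planned at the start, during follow-up and at the end, but PLAN FOR ANALYSING THE RESULTS gives it no analysis.

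**The concern.** A refraction can leave room for judgement, most of all when the reader has to choose between two neighbouring values. Here the reader knows that the child is treated and may see the previous value. Nothing in the plan requires the same device at each visit. An examiner who hopes the lens works may record no change when in doubt.

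In a concurrent trial with masked assessors, such a tendency would fall on both arms and largely cancel. Here the control readings were complete before this study began, so expectation about this lens cannot have affected them. Any such tendency would appear as myopia control. A larger sample would not help, because it shrinks the standard error and leaves the bias as it was.

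**Working it through.** **Inputs.** From SAMPLE AND SAMPLE SIZE: difference 0.25 D, SD 0.50 D, n = 31, loss 20%, 38 after loss, 50 planned ("The sample size will be 50 subjects of both genders"). From CURRENT STATE OF RESEARCH: 114 controls and a measurement step of 0.25 D. From PLAN FOR ANALYSING THE RESULTS: significance level 0.05. Assumed: two-sided testing and 80% power (neither is stated), and SD 0.50 D in both groups.

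**1. The plan's own figure.** The one-sample formula gives n = [0.50 × (1.960 + 0.842) / 0.25]² = 31.4, which matches 31. For loss, 31 × 1.2 = 37.2, rounded up to 38, as in "taking into account a 20% loss to follow-up the n should equal 38 subjects in the group". Dividing by 0.8 instead would give 39.

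**2. Does a 0.25 D step matter by itself?** Rounding to the nearest step q adds variance q²/12 per reading.
- Change in sphere (two readings): 2 × 0.0625/12 = 0.0104. The SD becomes √(0.25 + 0.0104) = 0.510 D and n = 32.7.
- Change in spherical equivalent (half the cylinder is added, so × 1.25): 0.0130. The SD becomes 0.513 D and n = 33.0.
- Power with 40 completers against 114 controls falls from 77.7% to 76.0% or 75.6%.
- In a simulation of one million children, the true mean change was -0.1990 D and the mean after rounding was -0.1992 D.

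Symmetric rounding therefore leaves the mean unbiased and costs about 2 patients, even if the SD of 0.50 D does not already contain it.

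**3. Does a directional reading matter?** Suppose a share f of the twelve-month readings is one step too favourable. The bias is f × 0.25 D. With 50 × 0.8 = 40 completers, the standard error of the difference is 0.50 × √(1/40 + 1/114) = 0.0919 D. With no true effect, the two-sided test rejects with probability 1 − Φ(1.96 − bias/0.0919) + Φ(−1.96 − bias/0.0919).

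| Share f (assumed) | Bias | Bias / standard error | False-positive rate |
|---|---|---|---|
| 10% | 0.025 D | 0.27 | 5.9% |
| 25% | 0.0625 D | 0.68 | 10.4% |
| 50% | 0.125 D | 1.36 | 27.5% |

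With all 50 children completing, the rates are 6.0%, 11.4% and 31.4%. They rise because the standard error falls while the bias stays.

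No passage supports any particular f. As step and target effect are both 0.25 D, bias divided by effect simply returns f, so that ratio is no evidence of size.

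**The case against.** **Step equal to effect.** A reader might infer from "progress -0.25 diopters in six months (the resolution limit of the measurement method" and "Statistical calculation for a difference of 0.25 diopters in progression with respect to controls" that the method is too coarse for the effect. The documents do not support this. The first figure concerns one child over six months and the second a difference in group means. Step 2 shows that the cost is small, and a 0.25 D change in cylinder moves the spherical equivalent by only 0.125 D.

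**The autorefractometer.** A reader might also infer that it goes unused or would give a finer reading. Neither is stated: it is listed, and its resolution is not given. What stands is that the protocol does not fix which device supplies the endpoint.

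**Direction.** Cautious physicians, working with a system built to flag progression, might over-call it. That is possible, and it is why the size is left open. Such bias too would fall on the treated group alone.

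**The controls.** The documents do not say how the 114 children were refracted, so other reading error there cannot be excluded. This narrows the claim to expectation about this lens.

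**Retention.** A reader might add that favourable readings also keep progressing children in the study. The HUMAN RESOURCES alert requires more than 0.25 D, so one doubtful step from no change does not trigger it. A true progressor who stays would later count against the lens. No second harm is claimed.

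**Rank and safeguard.** Progression is secondary, and axial length is already collected. Both limit the severity. But axial length has no defined analysis, and the documents give control progression in dioptres only.

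**Conclusion.** The concern holds as one of unmasked, unstandardised reading in a single treated group set against historical controls. It does not hold as one of insufficient resolution. The bias cannot be sized from the documents. Under the stated assumptions it ranges from negligible (10% of readings shifted, about 6% false positives) to serious (50% shifted, about 28%). The change should be made, but the primary objective of tolerance and adherence is untouched.

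Separately, the six-month rule that depends on this reading is worded in three ways: failure to arrest progression (CURRENT STATE OF RESEARCH), a result no better than expected without intervention (INCLUSION / EXCLUSION CRITERIA), and more than 0.25 D (HUMAN RESOURCES). These passages must be reconciled. No rule is proposed here.

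**What to change.** - **METHODS.** Define progression as the change in spherical equivalent from cycloplegic autorefraction. Use the mean of a fixed number of repeated readings, entered from the printout, with the same instrument for each child at baseline, six and twelve months, taken before the earlier value is opened. Add fields for instrument and readings to the visit forms. Refraction for prescribing is not affected.
- **Controls.** Establish from the group that followed the 114 children how they were refracted. If by another method, also report the comparison using the matching method. A constant offset between methods cancels in a within-child change; differences in noise or in examiner judgement do not.
- **PLAN FOR ANALYSING THE RESULTS.** Name the change in axial length as a supporting outcome. With no control value in the documents, it serves as a within-group check on whether the refraction result is credible.

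The cost is protocol and form wording; the equipment is already listed. The downside is that two versions of the refraction endpoint may have to be reported. The fix reduces examiner discretion but does not supply a concurrent control.
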